## **Occasion 2**

When arriving to the lab, the subject will confirm to not have eaten 2 hours and not have consumed caffeine or alcohol 3 hours prior to the experiment. Thereafter the subject will remove socks and lay down as the acclimatization period begins. A blood pressure cuff is placed around the upper arm as well as around the ankle. The EPOS-probes are placed within the marked skin areas from the previous measurement. A vacuum pillow is set up to position the arm and minimize movement artefacts. Once five minutes has passed, the subject's blood pressure and pulse are noted. Thereafter the PSI-X camera is set up and angled to film the plantar side of the foot from about 25 cm. The subject is asked to lay as still as possible during the measurement.

Once the acclimatization period has passed, the lights in the lab are turned off and the measurement will begin. Firstly, baseline data will be collected as the subject rest for 10 minutes without provocation. Thereafter the blood pressure cuff on the ankle will inflate to 250 mmHg for five minutes whilst data is collected. Lastly data is collected for five minutes after the blood pressure cuff deflates. Thereafter the PSI-X camera is moved and angled to film the forearm from a 25 cm distance. Baseline data will be collected on the arm as the subject rest for 10 minutes without provocation. Thereafter the blood pressure cuff on the upper arm will inflate to 250 mmHg for five minutes whilst data is collected and lastly data is

collected for five minutes after the blood pressure cuff deflates. The temperature within the room is noted before and after the measurement.

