## Objectives

The aim of this study is to learn more about the microcirculation in the skin by examining sex and age-related day-to-day variability in healthy subjects.

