## Methods

To study day-to-day variability, each subject's data will be collected on two separate occasions within 7 days.

### Occasion 1

Once arriving to the lab, the subject will answer the following questions by filling in a questionnaire:

1. The subjects age and gender.
2. If the subject is biologically female- Usage of anticonception medication?
3. If the subject is biologically female- Number of days since the first day of the subject's period cycle, alternatively number of years since the subject's most recent period cycle?
4. How many minutes a week does the subject engage in high intensity workout (such as running, football ect)?
5. How many minutes a week does the subject engage in low intensity workout (such as hiking, biking, gardening work ect)?
6. Conformation to not have eaten two hours and not used nicotine, caffeine, or alcohol three hours prior to the experiment.
7. Conformation that the subject do not have a chronic disease such as diabetes, rheumatism ect.

Once the questions are filled in, the subject will receive information about the experiment and gets the opportunity to ask questions, thereafter a consent form is signed. The subject's height and weight will be measured and BMI calculated. The subjects skin type will be determined using the Fitzpatrick scale.

An acclimatization period of 15 minutes begins and the subject will remove socks and lay down. While the subject rests the equipment will be set up. A blood pressure cuff is placed around the upper arm as well as around the ankle. An EPOS-probe is placed on the dorsal side of the foot as well as the volar side of the forearm. A marker pen is used to mark the skin around the probes which enables the probe to be placed on the same location on the next measurement. A vacuum pillow is set up to position the arm and minimize movement artefacts. Once five minutes has passed, the subject's blood pressure and pulse are noted. Thereafter the PSI-X camera is set up and angled to film the plantar side of the foot from about 25 cm. The subject is asked to lay as still as possible during the measurement.

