## Statistical analysis of Day-to-day variability

Median values from the baseline data of each measurement will be extracted for all parameters. The maximum value during the post-occlusive reactive hyperemia (PORH) will also be extracted for all parameters. See Table 1 and Table 2 for more details regarding which values will be included in the data analysis.

*Table 1. Values extracted from the EPOS data of each measurement.*

Time period	Conventional perfusion	Speed-resolved-perfusion -Low speed	Speed-resolved-perfusion -Medium speed	Speed-resolved-perfusion -High speed	Oxygen saturation	Vessel diameter	RBC tissue fraction
Baseline of foot (10 minutes)	Median	Median	Median	Median	Median	Median	Median
Occlusion of foot (5 minutes)	No value extracted	No value extracted	No value extracted	No value extracted	No value extracted	No value extracted	No value extracted
PORH in foot (5 minutes)	Peak value	Peak value	Peak value	Peak value	Peak value	Peak value	Peak value
Baseline of arm (10 minutes)	Median	Median	Median	Median	Median	Median	Median
Occlusion of arm (5 minutes)	No value extracted	No value extracted	No value extracted	No value extracted	No value extracted	No value extracted	No value extracted
PORH in arm (5 minutes)	Peak value	Peak value	Peak value	Peak value	Peak value	Peak value	Peak value

*Table 2. Values extracted from the PSI-X camera of each measurement.*

Time period	Conventional perfusion	Speed-resolved-perfusion -Low speed	Speed-resolved-perfusion -Medium speed	Speed-resolved-perfusion -High speed	Oxygen saturation
Baseline of foot (10 minutes)	Median	Median	Median	Median	Median
Occlusion of foot (5 minutes)	No value extracted	No value extracted	No value extracted	No value extracted	No value extracted
PORH in foot (5 minutes)	Peak value	Peak value	Peak value	Peak value	Peak value
Baseline of arm (10 minutes)	Median	Median	Median	Median	Median
Occlusion of arm (5 minutes)	No value extracted	No value extracted	No value extracted	No value extracted	No value extracted
PORH in arm (5 minutes)	Peak value	Peak value	Peak value	Peak value	Peak value

To identify potential sex- and age-related variability, Wilcoxon test will be conducted for non-normally distributed data and t-test for normally distributed data. To compare the data collected from the foot to the arm, Kruskal-Wallis or Anova will be used.

Since multiple comparisons between groups will be conducted, Bonferroni corrections will be done to reduce the risk of Type 1 error.

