## Motivation to the number of study-participants

12 participants in each group (men and women, age 20-30 years or 50-60 years), which adds up to a total of 48 participants, is chosen due to the tradition within the study field. In addition, we do not know if there is a difference among the four groups, which is why we chose a smaller study population.

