## Method for dealing with outliers

Outliers in the collected data caused by movement (and thereby considered artifacts) will be handled using the algorithm presented in reference 2 above.

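### Nicotine is in the pre-visit confirmation at occasion 1 but not at occasion 2, so as written nicotine use before the second visit is neither checked nor recorded

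*Protocol*

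**What the plan says.** The Protocol's Objectives give the aim as "examining sex and age-related day-to-day variability in healthy subjects". Its Methods section explains why there are two visits: "To study day-to-day variability, each subject's data will be collected on two separate occasions within 7 days".

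Item 6 of the occasion 1 questionnaire reads "Conformation to not have eaten two hours and not used nicotine, caffeine, or alcohol three hours prior to the experiment". Under Occasion 2 there is no reference back to that item. The condition is written out again: on arrival "the subject will confirm to not have eaten 2 hours and not have consumed caffeine or alcohol 3 hours prior to the experiment". The next step is "Thereafter the subject will remove socks and lay down as the acclimatization period begins"; no questionnaire is described at this visit.

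The SAP, under Statistical analysis of Day-to-day variability, plans group tests with no covariate: "To identify potential sex- and age-related variability, Wilcoxon test will be conducted for non-normally distributed data and t-test for normally distributed data". Its outlier section is limited to movement: "Outliers in the collected data caused by movement (and thereby considered artifacts) will be handled".

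**The concern.** The Protocol treats nicotine as a condition to control before the first measurement and then leaves it out of the check before the second. Staff who follow the Occasion 2 text would not ask about it. The occasion 1 answer cannot stand in, because it concerns the hours before a visit that may lie up to 7 days earlier.

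In a study of visit-to-visit variation, a condition controlled at one visit only enters the quantity being estimated. An effect of nicotine present only at the second visit would be counted as day-to-day variability. If such use were more common in one sex or age group, that group could appear more variable for a reason unrelated to sex or age, and without a record nobody could tell. The SAP does not define the between-visit measure, so the within-subject comparison of the two visits is inferred from the design.

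**Working it through.** **Side-by-side comparison of the two confirmations**

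| Item | Occasion 1 (questionnaire item 6) | Occasion 2 | Match |
|---|---|---|---|
| Food | 2 h | 2 h | yes |
| Caffeine | 3 h | 3 h | yes |
| Alcohol | 3 h | 3 h | yes |
| Nicotine | 3 h | not named | no |

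**Search for a safeguard elsewhere.** Nicotine, smoking and tobacco appear nowhere else in the available Protocol or SAP. There is no exclusion of users, no nicotine variable, no covariate and no sensitivity analysis. The outlier rule would not catch an exposed visit, and under the missing-data section such a visit would count towards the 48 complete sets.

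**Size.** The plan has no figure to reproduce. The SAP says the group size "is chosen due to the tradition within the study field", so no planning SD is available either. What follows is an illustration.

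Inputs:
- Group size 12 (Protocol, Design).
- *k*, the number in a group exposed before occasion 2 only; *p* = *k*/12. Assumed: 1 or 4.
- *δ*, the shift in the log of the measured value when exposed. Assumed: 0.2 to 0.4. This is not meant for oxygen saturation or vessel diameter.
- *s*, the true within-subject SD on the log scale. Assumed: 0.10, 0.15 or 0.20.

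The variance of the difference between visits is 2*s*² + *p*(1−*p*)*δ*². Halving it and taking the root gives the apparent within-subject SD:

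sqrt( *s*² + *p*(1−*p*)*δ*²/2 )

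For *k* = 1, *p*(1−*p*) = (1/12)(11/12) = 0.0764. The added term is 0.0764 × 0.04/2 = 0.00153 at *δ* = 0.2, and 0.0764 × 0.16/2 = 0.00611 at *δ* = 0.4. For *k* = 4, *p*(1−*p*) = (4/12)(8/12) = 0.2222, and the added terms are 0.00444 and 0.01778.

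| *k* | *s* | Apparent SD, *δ* = 0.2 | Apparent SD, *δ* = 0.4 | Inflation |
|---|---|---|---|---|
| 0 | any | unchanged | unchanged | 0% |
| 1 | 0.10 | 0.107 | 0.127 | +7% to +27% |
| 1 | 0.15 | 0.155 | 0.169 | +3% to +13% |
| 1 | 0.20 | 0.204 | 0.215 | +2% to +7% |
| 4 | 0.15 | 0.164 | 0.201 | +9% to +34% |

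These figures leave out the mean shift between visits, *pδ*: 0.017 to 0.033 for *k* = 1 and 0.067 to 0.133 for *k* = 4. A variability measure that keeps the mean shift, such as the sum of squared differences divided by 2*n*, replaces *p*(1−*p*) by *p*. For *k* = 4, *s* = 0.15 and *δ* = 0.4 it gives sqrt(0.0225 + 0.3333 × 0.16/2) = sqrt(0.0492) = 0.222, or +48%. The answer therefore also depends on a measure that the SAP has not defined.

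**The case against.** The mismatch itself is hard to dispute. The case on the other side concerns its weight.

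- **It is probably a drafting slip.** The other three items keep identical windows, and nothing suggests that different conditions were intended. This is likely right. It makes the correction uncontroversial but does not supply the missing check.
- **Occasion 2 leans on occasion 1 in places.** For example, it mentions acclimatization without repeating the 15 minutes, and the participant has met the nicotine condition within the past week. That makes use before the second visit less likely. Because the other three items are written out again in full, shorthand is not a full explanation.
- **Participant information may mention nicotine.** It is not in the text available, so this cannot be ruled out. The Occasion 2 text is silent; it does not permit nicotine. An instruction to participants would still not be a check or a record at the visit.
- **Lack of recording is not peculiar to nicotine.** No form is described at occasion 2 for any of the items, and the occasion 1 item captures a statement of abstinence, not habitual use. This stands. What is specific to nicotine is the missing confirmation.
- **Harm needs a chain of conditions.** There must be users in the sample, use in the three hours before occasion 2 only, an effect on the measurements and, for group bias, imbalance by sex or age. The documents quantify none of these, and four exposed out of 12 has no basis in them. This also stands, and it is why the illustrative percentages carry no weight in the conclusion.

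**Conclusion.** The concern holds. As the Protocol is written, the two visits run under different pre-measurement checks, and no analysis rule in the SAP would reveal or correct the consequence. The true size is unknown and may be zero.

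The conclusion rests on the Protocol's own decision to control nicotine at the first visit and on reading the study as a within-subject comparison of the two visits. It does not rest on any outside evidence about nicotine or on the illustrative figures. This is not a fatal flaw, but it should be corrected: it affects the conditions on which the stated aim depends, and exposure that goes unrecorded may not be recoverable later.

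**What to change.** Reconcile questionnaire item 6 and the Occasion 2 text so that both visits use the same confirmation, including nicotine, and record the answer at each visit. The prospective cost is one word in the Protocol and one yes/no entry on the visit record, with no added procedure.

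If second visits have already taken place, ask those participants about nicotine use before occasion 2. This costs some contact time, and the answers depend on recall, so it should be done soon. Only if some were exposed, add a sensitivity analysis that leaves out those participants' visit pairs. Each omission reduces a group of 12 by one. If recruitment is still open, the SAP's rule of recruiting until 48 complete sets are obtained leaves room to consider replacement.

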### Document revision history

Issue	Summary of change
01	New document

## Statistical program

The statistical analysis will be conducted in IBM SPSS (SPSS, Chicago, IL).

## Statistical analysis of Day-to-day variability

Median values from the baseline data of each measurement will be extracted for all parameters. The maximum value during the post-occlusive reactive hyperemia (PORH) will also be extracted for all parameters. See Table 1 and Table 2 for more details regarding which values will be included in the data analysis.

*Table 1. Values extracted from the EPOS data of each measurement.*

Time period	Conventional perfusion	Speed-resolved-perfusion -Low speed	Speed-resolved-perfusion -Medium speed	Speed-resolved-perfusion -High speed	Oxygen saturation	Vessel diameter	RBC tissue fraction
Baseline of foot (10 minutes)	Median	Median	Median	Median	Median	Median	Median
Occlusion of foot (5 minutes)	No value extracted	No value extracted	No value extracted	No value extracted	No value extracted	No value extracted	No value extracted
PORH in foot (5 minutes)	Peak value	Peak value	Peak value	Peak value	Peak value	Peak value	Peak value
Baseline of arm (10 minutes)	Median	Median	Median	Median	Median	Median	Median
Occlusion of arm (5 minutes)	No value extracted	No value extracted	No value extracted	No value extracted	No value extracted	No value extracted	No value extracted
PORH in arm (5 minutes)	Peak value	Peak value	Peak value	Peak value	Peak value	Peak value	Peak value

*Table 2. Values extracted from the PSI-X camera of each measurement.*

Time period	Conventional perfusion	Speed-resolved-perfusion -Low speed	Speed-resolved-perfusion -Medium speed	Speed-resolved-perfusion -High speed	Oxygen saturation
Baseline of foot (10 minutes)	Median	Median	Median	Median	Median
Occlusion of foot (5 minutes)	No value extracted	No value extracted	No value extracted	No value extracted	No value extracted
PORH in foot (5 minutes)	Peak value	Peak value	Peak value	Peak value	Peak value
Baseline of arm (10 minutes)	Median	Median	Median	Median	Median
Occlusion of arm (5 minutes)	No value extracted	No value extracted	No value extracted	No value extracted	No value extracted
PORH in arm (5 minutes)	Peak value	Peak value	Peak value	Peak value	Peak value

To identify potential sex- and age-related variability, Wilcoxon test will be conducted for non-normally distributed data and t-test for normally distributed data. To compare the data collected from the foot to the arm, Kruskal-Wallis or Anova will be used.

Since multiple comparisons between groups will be conducted, Bonferroni corrections will be done to reduce the risk of Type 1 error.

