## Design

Prospective observational study. In the study, four groups will be compared: Men aged 20-30 years, women aged 20-30 years, men aged 50-60 years and women aged 50-60 years. In total 48 participants will be included- 12 from each group.

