## Method for dealing with missing data

The goal is to have 48 complete set of data collection for the variability analysis and recruitment to the study will continue until this is achieved. Flowmotion analysis is more sensitive to artefacts, which most likely will be discovered late in the process once the recruitment to the study already is complete. Therefore we expect to exclude some measurements and most likely will not reach 48 complete sets of flowmotion signals.

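### The sole aim is sex- and age-related day-to-day variability, but no between-visit measure is defined, and the planned tests, read naturally, compare levels

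*SAP*

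**What the plan says.** The Protocol (Objectives) sets one aim, which it pursues by "examining sex and age-related day-to-day variability in healthy subjects". Under Methods, each participant's "data will be collected on two separate occasions within 7 days", and the stated reason is to study day-to-day variability. Under Design: "In total 48 participants will be included- 12 from each group".

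The SAP section Statistical analysis of Day-to-day variability begins with extraction: "Median values from the baseline data of each measurement will be extracted for all parameters". The peak during post-occlusive reactive hyperemia (PORH) is also taken. It continues: "See Table 1 and Table 2 for more details regarding which values will be included in the data analysis". Every filled cell in those tables is a median or a peak from a single measurement. The tests follow: "To identify potential sex- and age-related variability, Wilcoxon test will be conducted for non-normally distributed data and t-test for normally distributed data". On multiplicity: "Since multiple comparisons between groups will be conducted, Bonferroni corrections will be done to reduce the risk of Type 1 error".

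The section Method for dealing with missing data mentions the analysis once more, without defining it: "The goal is to have 48 complete set of data collection for the variability analysis".

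**The concern.** Day-to-day variability is the spread of a person's values between visits. To compare it by sex and age, the two visits must first be combined into a measure of that spread. Neither document does this. There is no visit difference, absolute difference, within-subject SD, coefficient of variation, intraclass correlation, limits of agreement or visit term. The SAP does not say which variable is tested, whether the tests are paired, or what happens to the second visit.

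Three things are at stake:

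- If the tabled values are tested, a difference in level can be reported as a sex or age difference in variability.
- A true difference in day-to-day variability can go unseen.
- On any reading, the tested variable is open and could be settled after the data are known.

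**Working it through.** **Inputs from the documents.** There are 4 groups of 12 (4 × 12 = 48 participants), two visits and a significance level of 0.05. The tables give 7 EPOS parameters × 2 sites × 2 periods = 28 values and 5 PSI-X parameters × 2 × 2 = 20 values, so 28 + 20 = 48 values per visit. The sample size rests on tradition in the field, so there is no power figure to reproduce.

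**Assumed inputs.** The documents give no SDs or effect sizes and no number of comparisons. I assume two-sided tests, normal data on the log scale, between-subject SD 0.4 and a lower within-subject SD of 0.10 in step 2. Bonferroni divisors are 6 (group pairs, 4 × 3 / 2) or 48 (extracted values). Rejection rates come from 10,000 simulated trials each, 12 v 12. Rank-sum ranges cover asymptotic and exact p-values.

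**Step 1: what each reading estimates.** Let y(i,v) = μ(group) + b(i) + e(i,v), with within-subject SD σw, and d(i) = y(i,1) − y(i,2).

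| Variable tested | Group contrast reflects | Informative on σw? |
|---|---|---|
| Tabled values or visit means | difference in μ | no |
| Visit 1 v visit 2, paired | mean visit shift | no |
| Signed d between groups | difference in mean shift | no |
| Absolute d, centred on group mean | SD(d) = √2·σw | yes |

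**Step 2: variability differs, means equal.** The within-subject SD is 0.10 in one group and 0.15, 0.20 or 0.30 in the other.

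| Test | Ratio 1.5 | Ratio 2 | Ratio 3 |
|---|---|---|---|
| Level, paired or signed-d tests, at 0.05 | 4-6% | 4-6% | 4-6% |
| Rank-sum, centred absolute d, at 0.05 | 17% | 40% | 74% |
| same, at 0.05/6 | 4-5% | 14-18% | 41-48% |
| same, at 0.05/48 | about 1% | 3-5% | 14-20% |
| t-test, centred absolute d, at 0.05 | 21-22% | 50-51% | 85% |

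The first row is no better than the false-positive rate. With equal variability, the centred tests reject 5-6% at 0.05.

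**Step 3: levels differ, variability equal (σw = 0.20 in both groups).**

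| Level tests on visit means | Gap 0.2 | Gap 0.5 |
|---|---|---|
| at 0.05 | 17-21% | 74-79% |
| at 0.05/6 | 4-6% | 42-52% |
| at 0.05/48 | about 1% | 13-24% |

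Check for the t-test: SD of a visit mean = √(0.4² + 0.20²/2) = √0.18 = 0.424. Noncentrality = gap / (0.424 × √(2/12)) = 0.2/0.173 = 1.15 and 0.5/0.173 = 2.89. Exact noncentral-t power is 19.7% and 78.8%, in line with the simulation.

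**Step 4: why the differences need centring.** Take equal variability (σw = 0.20) and a visit shift of 0.2, 0.3 or 0.4 in one group only. Rank-sum on uncentred absolute d rejects in 8%, 23% and 51%; on centred absolute d it rejects in about 5%.

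**Step 5: a further risk.** The SAP neither states nor excludes stacking both visits as independent values. If that were done, the variance of a group mean would be understated by a factor 1 + ICC. Simulated false positives at the 5% level are 11-16% for ICC 0.5 to 0.9. A normal approximation agrees: 1.96/√1.5 = 1.60 gives 11%, and 1.96/√1.9 = 1.42 gives 16%.

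**Sensitivity.** With between-subject SD 1, within-subject SD 0.5 v 1.0 and 20,000 replicates, the level t-test rejects 5.0%. On uncentred absolute differences the t-test rejects 50% and the rank-sum 40%. The contrast does not depend on the SDs in steps 2 and 3.

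**The case against.** The best defence is that the plan is under-specified rather than wrong. The section heading and the purpose of the two visits suggest that visit differences were meant. An unqualified Wilcoxon test can be the paired signed-rank test. A Wilcoxon or t-test on absolute visit differences would answer the aim, and the SAP does not rule it out. This stands in part: the level reading is the natural one, because the tables list the values that enter the analysis and Bonferroni is tied to comparisons between groups, but the text does not settle it. The point survives, because the paired and signed-difference readings also miss the size of variability, and the one reading that works is nowhere defined.

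The simulation inputs are assumptions, so the rates illustrate and do not measure this trial. That is true. What does not depend on them is that a test of means has no power above its significance level for a pure difference in within-subject spread.

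Log scale and centring are choices that the documents do not dictate, and a systematic visit shift could be counted as part of day-to-day variability. This is fair; reporting the shift separately keeps that information.

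The remedy also has little power under a wide Bonferroni family. If all 6 pairs are tested on all 48 values (6 × 48 = 288), power at SD ratio 2 is about 0.4% for rank-sum and 1% for the t-test, and 3-6% at ratio 3. This stands, and it is why estimates with intervals should lead.

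**Conclusion.** The concern holds, and it should be resolved before analysis because it touches the only stated aim. That no between-visit measure is defined is certain from the text. That the tests compare levels is the natural reading but not the only one; the paired and signed-difference readings fail as well. On the assumed variances with 12 per group at 0.05, the size of the problem is the difference between no power above the false-positive rate and 40-51% power when one group's within-subject SD is doubled. In the other direction, the level tests reject in up to 79% of trials in which variability does not differ at all.

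**What to change.** In the SAP section Statistical analysis of Day-to-day variability:

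1. Define for each endpoint and participant d(i) = ln(visit 1) − ln(visit 2), with the raw difference for oxygen saturation.
2. Report the mean visit shift per group separately.
3. Centre d(i) on its group's mean shift. Report the within-subject SD, SD(d)/√2, or the corresponding CV, per group with a 95% confidence interval.
4. Test sex and age effects on the absolute centred differences with the two-sample t-test or Wilcoxon rank-sum test, keeping Bonferroni and stating which comparisons form its family.
5. Keep level comparisons as a separately labelled analysis on each participant's mean of the two visits. ICC or limits of agreement are optional.

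An F-test on d is more powerful under normality (24%, 59% and 94% at ratios 1.5, 2 and 3), but it rejects 13% under the null with t(5)-distributed differences, so I would not use it.

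The cost is SAP wording and a little more analysis; no new data, visits or participants. The drawback is precision. With 12 per group (11 df) the 95% interval for a within-subject SD runs from √(11/21.92) = 0.71 to √(11/3.816) = 1.70 times the estimate. Power is low for modest ratios, so the SDs or CVs with their intervals should carry the conclusion. Pooling over the other factor (24 v 24, centred within the four groups) raises rank-sum power at ratio 2 from 40% to 70% at 0.05.

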## Significance level

Significance level is set to  $p < 0.05$ .

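### The sex and age tests compare levels or mean day shifts, so they do not analyse day-to-day variability; the contrasts and the Bonferroni family are also left open

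*SAP*

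**What the plan says.** The protocol's Objectives section gives the aim as "examining sex and age-related day-to-day variability in healthy subjects". Its Design section states that "four groups will be compared: Men aged 20-30 years, women aged 20-30 years, men aged 50-60 years and women aged 50-60 years", with 12 participants in each, and its Methods section that "data will be collected on two separate occasions within 7 days".

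In the SAP section on day-to-day variability, Tables 1 and 2 list a baseline median and a post-occlusion peak for each parameter at foot and arm, taken from each measurement. The sex and age analysis is one sentence: "To identify potential sex- and age-related variability, Wilcoxon test will be conducted for non-normally distributed data and t-test for normally distributed data". ANOVA or Kruskal-Wallis is named only for foot against arm. Error control is also one sentence: "Since multiple comparisons between groups will be conducted, Bonferroni corrections will be done to reduce the risk of Type 1 error". The SAP gives no divisor and names no primary endpoint. On the threshold it says "Significance level is set to" p < 0.05.

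**The concern.** The two occasions are the only source of information on day-to-day variability, yet nothing in the SAP combines them. There is no within-person difference, coefficient of variation, intraclass correlation or occasion term. The tests are not said to be paired or unpaired, and the groups that enter them are not named. An analyst who follows the text could complete every listed test without answering the question in the Objectives. A null result would say nothing about variability, and a significant one could be misread as being about it.

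Two secondary matters affect how any result is read. The 2x2 layout of sex and age has no matching model. The Bonferroni sentence can be applied within each endpoint or across all tests, with very different consequences, and the choice could be made after the data are seen.

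**Working it through.** **Inputs.** Four groups of 12 (protocol, Design), and 4 x 12 = 48 participants, which reproduces the SAP's total. The SAP gives no effect size, SD or power, so there is no power figure to reproduce. Two occasions per person (protocol, Methods). Alpha 0.05, taken as two-sided (assumption).

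**Endpoints and tests** (SAP Tables 1 and 2)
- EPOS: 7 parameters x 2 sites x 2 periods = 28.
- PSI-X: 5 x 2 x 2 = 20.
- Total: 28 + 20 = 48 endpoints.
- Pairwise group contrasts: 4 x 3 / 2 = 6 per endpoint, so 48 x 6 = 288.
- Sex and age main effects: 48 x 2 = 96.

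**What each test can detect.** Write a value as group mean + person effect + day effect, where the day effect has SD s_g in group g. The day difference d = occasion 2 - occasion 1 then has mean 0 and variance 2 x s_g^2.
- A paired test within a group tests mean(d) = 0, which holds whatever s_g is. It compares no sexes or ages.
- A between-group test on levels tests equal means, which also holds whatever s_g is.
- A between-group test on signed d tests equal mean shifts, with the same result.
- The mean of |d| is proportional to s_g, so a comparison of absolute differences does respond.

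Simulation (normal data, equal means, between-person SD 1, men's day-to-day SD 0.5 or 1.0):

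| Test at 0.05 | Women's day-to-day SD relative to men's | Rejection |
|---|---|---|
| Paired t-test, 12 women | 2, 3 or 4 times | 4.8-5.0% |
| 12 v 12 t-test on levels | 2, 3 or 4 times | 5.0-5.6% |
| t-test on signed d, 12 or 24 per group | 2 times | about 5% |
| t-test on absolute d, 12 v 12 | 2 times | 50% |
| t-test on absolute d, 24 v 24 | 2 times | 84% |

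These are t-tests. The rank versions also target a shift in location, so the argument carries over, but no figure was computed for them.

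**Layout.** In SD units of the outcome, the SE is sqrt(2/12) = 0.408 for a 12 v 12 contrast and sqrt(2/24) = 0.289 for a main effect. By noncentral t, the difference detectable with 80% power at 0.05 is 1.20 SD (22 df) against 0.83 SD (44 df). If pooled 24 v 24 tests are meant, the loss is small: for levels with 1.0 SD effects of both factors, power is 88% against 92% for the factorial model.

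**Error family.**
- Within each endpoint: 0.05/6 = 0.0083 per contrast. On null data for levels, the chance of at least one false-positive endpoint among 48 is about 87% / 60% / 20% at assumed between-endpoint correlation 0 / 0.5 / 0.9.
- Over all tests: 0.05/288 = 0.00017. Error is held, but 12 v 12 power at 1.0 SD is about 5%.

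**Choice of variability outcome** (sex main effect in the factorial model, two-fold SD ratio, 0.05, normality)
- Log of the absolute day difference: 58%.
- Untransformed absolute difference: 84%.
- Absolute deviation of d from its group median: about 76%.

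Uncentred differences mix a systematic day shift with variability. If only women shift by 1 SD and the SDs are equal, the log version rejects in 29% and the centred version in about 4%. If both sexes shift by 1 SD of the men's day difference, power of the log version falls from 58% to 25%.

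**The case against.** The strongest reply is that this is a small exploratory study. The SAP says "we do not know if there is a difference among the four groups" and makes no confirmatory claim. The section heading shows that day-to-day variability is intended, so a reasonable analyst would form day differences. That intention is clear, but no such outcome is written down, and the most natural version, a test on signed differences, would still miss the aim. Exploratory status is a fair reason not to insist on strict error control over every endpoint. It does not supply the missing outcome, and the SAP does commit to significance tests and Type 1 error control.

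On error control, a reader might infer that the SAP uses the wrong Bonferroni divisor and so has a family-wise error near 87%. The documents do not support that. The sentence gives comparisons between groups as its reason but does not exclude endpoints from the divisor. The high figure also needs uncorrelated endpoints, which is implausible for parameters from the same two devices. What stands is that the family is not stated.

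A reader might also infer that the 2x2 design is wasted. That holds only if 12 v 12 contrasts are meant. The four-group wording leans that way, but the SAP does not settle it, and with pooled tests little power is lost.

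**Conclusion.** The main point holds: the sex and age analysis as written does not address the stated aim. Applied to the listed medians and peaks, it rejects at about its false-positive rate even when variability differs two- to four-fold. That size rests on normal data and equal means, but the reason is structural: these tests concern location, and the question concerns spread. The data to be collected can answer it.

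The two secondary points are gaps in specification. The unused layout matters materially only under the 12 v 12 reading (1.20 against 0.83 SD detectable). The undefined family leaves the error rate anywhere from controlled to about 87%, depending on a reading and on correlations that the documents do not give. The SAP should be amended before analysis.

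**What to change.** In the SAP section on day-to-day variability:

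1. **Outcome.** For each endpoint compute d = occasion 2 - occasion 1 per participant, with the scale (raw or log) fixed in advance for each parameter. Subtract the median of d in the participant's sex-by-age group and use the untransformed absolute deviation as the variability outcome. Report the mean shift from day 1 to day 2 separately. If levels are compared, use the mean of the two occasions as a separate secondary outcome.
2. **Model.** Fit one sex-by-age model per endpoint to all 48 participants. Report sex and age main effects with 95% CIs. Give the interaction and the 12 v 12 contrasts as descriptive follow-up; the interaction has SE sqrt(4/12) = 0.577 SD and would need 1.65 SD for 80% power at 0.05.
3. **Family.** Either name one primary endpoint, with 0.025 for each main effect and everything else labelled exploratory, or correct over the 96 main-effect tests.

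The change needs no new data. It will give fewer significant results, and only large differences in variability are detectable. By noncentral t (normal outcome, equal SDs, so approximate here), the main effect detectable with 80% power rises from 0.83 SD at 0.05 to 0.92 SD at 0.025 and 1.34 SD at 0.05/96. Centring lowers power at a two-fold ratio from 84% to about 76%. In return, a systematic day shift is not read as variability.
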